• The effect of alvelestat on disease progression	
By treatment group (alvelestat/placebo):
 
 • Proportion of subjects alive and free of respiratory failure (without need for non-invasive or invasive mechanical ventilation, high flow oxygen, or Extracorporeal Membrane Oxygenation (ECMO) at Day 29

Objective	Endpoint

 The effect of alvelestat on clinical outcomes 	By treatment group (alvelestat/placebo): 
 Mortality rate at Day 90 safety endpoint Proportion of subjects alive and free of respiratory failure (without need for non-invasive or invasive mechanical ventilation, high flow oxygen, or ECMO) at Days 5, 10 and 60 Length of hospital stay Length of ICU stay Time to room air (those on supplemental oxygen at Baseline)

 The effect of alvelestat on disease severity 	By treatment group (alvelestat/placebo): 
 Percentage of patients deteriorating (>1 and >2 increase in WHO 9-point ordinal scale*) at Day 5, Day 10, Day 29 and Day 60 Percentage of patients improving (>1 and > 2 decrease in WHO 9-point ordinal scale) at Day 5, Day 10, Day 29 and Day 60

 To explore Pharmacokinetics (PK) in patients with COVID-19 	
 Plasma PK (sparse sampling taken pre or 1-2 hours post study drug dosing) in participants randomized to alvelestat.

* WHO 9-point ordinal scale:

0. Uninfected, no clinical or virological evidence of infection
1. Ambulatory, no limitation of activities
2. Ambulatory, limitation of activities
3. Hospitalized – mild disease, no oxygen therapy
4. Hospitalized – mild disease, oxygen by mask or nasal prongs
5. Hospitalized – severe disease, noninvasive ventilation or high flow oxygen
6. Hospitalized – severe disease, intubation and mechanical ventilation
7. Hospitalized – severe disease, ventilation and additional organ support – vasopressors, renal replacement therapy, extracorporeal membrane oxygenation
8. Death

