2.0 SCHEDULE OF ASSESSMENTS (SOA)

a) For subjects completing treatment at Day 5

Study period	Screening Period	Study Treatment Period (once daily assessment for safety, respiratory support requirement ⁷ , level of hospital care [ward/ICU] and adverse events during hospitalization) ²					Safety and Efficacy Follow Up Period ²		
Visit Name	Screening	Baseline/ Randomize			End of Treatment (EoT) ⁸	Safety Follow Up (FU)	Clinical Outcome Assessment (COA)	Final Safety Follow Up (FU) 2	Mortality Follow Up
Study Day	Day-2 to Day -1 (screening and randomization can be on same day)	Day 1	Day 2	Days 3 and 4	Day 5	Day 10 (+/- 2 days)	Day 29 (+/- 2 days)	Day 60 (+/- 4 days)	Day 90 (+/- 7 days)
Eligibility check	X								
Informed consent	X								
Medical History	X								
Randomization		X							
Physical exam (full at screening, limited thereafter)	X	X	X	X	X	X			
Study Drug dosing		X	X	X	X				
Interim history, concomitant med, and adverse event recording ^{1, 2}	X	X	X	X	X	X	X ⁵	X ⁵	
Prospective headache query		X			X				
Pregnancy test (high sensitivity serum at screening, urine thereafter) ⁹	X					X			
Blood draw (screening and in-study safety monitoring) ^{2, 9}	X	X			X	X			

Visit Name	Screening	Baseline/ Randomize			End of Treatment (EoT)	Safety Follow Up (FU)	Clinical Outcome Assessment (COA)	Final Safety Follow Up (FU) 2	Mortality Follow Up
Study Day	Day-2 to Day -1 (screening and randomization can be on same day)	Day 1	Day 2	Days 3 and 4	Day 5	Day 10 (+/- 2 days)	Day 29 (+/- 2 days)	Day 60 (+/- 4 days)	Day 90 (+/- 7 days)
Blood draw (biomarkers)		X			X				
SaO ₂ /FiO ₂		X	X	X	X				
Blood (PK) ³		X			X ⁶				
EKG ^{2,4}	X	X			X ⁶				
Progression Endpoint (alive and free of respiratory failure, respiratory support level ⁷)					X	X		X ⁵	
Clinical outcomes assessments including WHO ordinal scale assessment		X	X	X	X	X	X	X ⁵	X ^{5,10}

¹ Only SAEs to be collected prior to randomization

² Investigations and examination performed as part of routine clinical assessment of COVID-19 may be used for eligibility and in study safety, adverse event and respiratory support requirement assessment

³ Time of PK and last dose of study medication prior to PK to be recorded in CRF

⁴ EKG to be taken 1-2 hours after study drug dosing when feasible

⁵ Telehealth visit if hospital discharge occurs before scheduled visit

⁶ PK and EKG can be taken on any one of Days 3-5

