4.0 OBJECTIVES AND ENDPOINTS

Objective	Endpoint
Primary	
By treatment group (alvelestat/placebo):
 
 • Numbers and % of subjects who experience at least 1 treatment-emergent adverse event to Day 60 (Safety Outcome Assessment) • Adverse events of special interest (liver function abnormalities, corrected QT interval, infections, and neutropenia) and clinically significant safety monitoring labs tests to Day 14 (acute treatment period) or EoT • Number and % of subjects that discontinue alvelestat to Day 5 or 10 • Number and % of subjects requiring dose reduction to Day 5 or 10 • Number and % of subjects with AE of headache on prospective questioning and CTCAE severity Grade to Day 5 or 10 • Change in vital signs, EKG, safety laboratory measures to Day 5 or 10 or EOT
Secondary	
By treatment group (alvelestat/placebo), change from baseline to Day 5 or 10 in:
 
 • Blood biomarkers of NETosis (cell-free DNA; citrullinated histone H3; Myeloperoxidase (MPO)-DNA complexes) • Blood biomarkers of inflammation (absolute neutrophil count; absolute lymphocyte count; neutrophil-lymphocyte ratio [NLR], C-Reactive protein, procalcitonin) • Pro-inflammatory cytokines IL-1beta, IL-6, IL-8, TNF-alpha) • Coagulopathy as measured by D-Dimer • Plasma desmosine/isodesmosine

[figure not shown]
Objective	Endpoint

 To explore the effect of alvelestat on pulmonary function 	By treatment group (alvelestat/placebo): 
 Change from baseline to Day 5 or 10, or EoT in SaO₂/FiO₂

 The effect of alvelestat on disease progression 	By treatment group (alvelestat/placebo): 
 Proportion of subjects alive and free of respiratory failure (without need for non-invasive or invasive mechanical ventilation, high flow oxygen, or Extracorporeal Membrane Oxygenation (ECMO) at Day 29

 The effect of alvelestat on clinical outcomes 	By treatment group (alvelestat/placebo): 
 Mortality rate to Day 90 safety endpoint Proportion of subjects alive and free of respiratory failure (without need for non-invasive or invasive mechanical ventilation, high flow oxygen, or ECMO) at Days 5, 10 and 60 Length of hospital stay Length of ICU stay Time to room air (those on supplemental oxygen at Baseline)

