5.0 STUDY DESIGN

5.1 Overall Design and Purpose

This is a Phase Ib/II single-center, 2:1 randomized, blinded, placebo-controlled, parallel group, first in disease study. The purpose is to determine the safety, tolerability and PK and explore the mechanistic and clinical effect of alvelestat 240mg orally twice per day for 5 or 10 days added to standard of care in adult patients (≥ 18 years) with COVID-19 respiratory disease.

The study is divided into 3 periods: a screening period, treatment period, and follow up period ([Figure 1](#))

Figure 1: Study Schematic

- **A screening period** from Day -2 to randomization. Eligibility assessments and written informed consent will occur prior to randomization and treatment arm allocation. Serious Adverse Events will be collected during screening.
- **A treatment period** consisting of alvelestat/matched placebo 240 mg/matched placebo bid Days 1 to 5 given on top of standard of care (SoC – per local clinical guidelines). Safety assessments including vital signs, liver and renal function, EKG, and hematology will be assessed at baseline, then as per the Schedule of Assessments (SoA) for the remainder of the 5-day treatment period. Adverse events, vital signs, respiratory support and concomitant medications that may be part of routine clinical care will be collected daily during hospitalization. Blood will be collected at baseline and during study drug treatment to Day 5 for secondary efficacy biomarkers, along with assessment of oxygen deficit assessments (SaO₂/FiO₂). PK sampling will be collected on 2 occasions, at initiation of dosing and at end of treatment (EoT) for steady state analysis. For patients that remain hospitalized at Day 5 due to COVID-19, an optional extension period of treatment to Day 10 may be given and can be referred to on the separate SOA covering this extension. Clinical outcomes of disease progression (respiratory support requirements), disease severity (WHO ordinal scale), will be completed at Baseline (Day 1), during the treatment period to (Day 5 or 10), or EoT and to Day 60 (Clinical Outcome Assessments). Those subjects who are unable to complete the treatment period for any reason, including those discharged from hospital prior to completion of Day 5 or 10, will discontinue study drug and undergo an EoT assessment. Wherever possible they will continue to be followed up in the study.

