- **A follow-up period** from Day 5 or 10/EoT to Day 90. This is for safety testing to end of systemic drug exposure (Day 10 for 5-day study, Day 15 for 10-day study or 5 days after EoT), to Day 60 for longer term safety and to Day 90 for mortality data collection, for the Clinical Outcome Assessments (COA) to Day 60) and mortality (Day 90). Visits after Day 10 or Day 15 (or 5 days +/- 2 days after last dose), may be by telehealth visits. Adverse events, vital signs, respiratory support and concomitant medications that may be part of routine clinical care will be collected daily during hospitalization and to the Day 29 and Day 60 assessments (may be collected by telehealth call).

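### The Progression Endpoint row of the Schedule of Assessments omits Day 29, the day that defines the disease-progression endpoint, although the status is largely recoverable from the Day 29 WHO score

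*Protocol*

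**What the plan says.** The Synopsis and Section 4.0 of the protocol give the disease-progression objective a single endpoint, the share of subjects who are living and have no respiratory failure, with the time point fixed as "high flow oxygen, or Extracorporeal Membrane Oxygenation (ECMO) at Day 29". The same outcome at the other days, "high flow oxygen, or ECMO) at Days 5, 10 and 60", is listed separately under clinical outcomes. SAP Table 3 also carries the Day 29 endpoint, but sets it against the pulmonary-function objective.

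Section 2.0 of the protocol has two schedule tables: a) for subjects finishing treatment at Day 5, and b) for those extending to Day 10. Each contains a row headed "Progression Endpoint (alive and free of respiratory failure, respiratory support level". In table a) it is marked at Days 5, 10 and 60, and in table b) at Days 10 and 60. A separate row, "Clinical outcomes assessments including WHO ordinal scale assessment", is marked at Day 29 in both tables.

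The text of Section 5.1 goes further than the Progression Endpoint row. Its follow-up paragraph says that respiratory support, among other items, "will be collected daily during hospitalization and to the Day 29 and Day 60 assessments (may be collected by telehealth call"). Its treatment-period paragraph begins the collection earlier: "Clinical outcomes of disease progression (respiratory support requirements), disease severity (WHO ordinal scale), will be completed at Baseline (Day 1"). Section 9.0 makes adherence to the schedule mandatory.

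**The concern.** The row named after the progression endpoint covers the days on which the outcome is a supporting measure and leaves out the one day on which it is the endpoint of its own objective. Text and table disagree, and because Section 9.0 makes the schedule binding, the site cannot simply treat the table as secondary.

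Section 9.3.1 defines progression as a status recorded in its own right: alive and free of respiratory failure, or alive with it. If the case report form is built from this row, that item will not appear at Day 29. The analyst would then have to derive it from another variable by a rule that neither document states. This matters most for discharged patients. Section 5.4 puts the mean hospital stay at 5 days, so many patients may be at home by Day 29, where a WHO score of 1 or 2 grades activity limitation and does not record respiratory support.

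**Working it through.** The plan has no figure to reproduce. The check sets the schedule against the endpoint definition, asks what the other Day 29 data provide, and then sizes the residual risk.

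**1. Days required and days scheduled**

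| Source | Day 1 | Day 5 | Day 10 | Day 15 | Day 29 | Day 60 |
|---|---|---|---|---|---|---|
| Endpoint definitions (Synopsis, 4.0) | no | yes | yes | no | yes | yes |
| Progression Endpoint row, table a) | blank | X | X | no column | **blank** | X |
| Progression Endpoint row, table b) | no column | no column | X | blank | **blank** | X |
| Clinical outcomes/WHO row, table a) | X | X | X | no column | X | X |
| Clinical outcomes/WHO row, table b) | no column | no column | X | X | X | X |

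The adverse-event row and the clinical outcomes row both fall under the expected visits in each table and both have a Day 29 mark. The blank is therefore not a shifted column.

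**2. Can the WHO score supply the Day 29 status?** The protocol counts non-invasive ventilation, invasive ventilation, high-flow oxygen and ECMO as respiratory failure. Set against the scale in Section 9.3.2:

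- Scores 0-4 cover no infection, ambulatory patients, and hospitalized patients on no oxygen or on mask or prongs. These are alive and free of respiratory failure.
- Scores 5-7 cover non-invasive ventilation or high-flow oxygen, intubation, and ventilation with organ support including ECMO. These are respiratory failure.
- Score 8 is death.

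The cut 0-4 versus 5-8 therefore gives the binary endpoint. Ordinary oxygen at home does no harm, because it still counts as free of respiratory failure. The one gap is a patient on high-flow or non-invasive support outside hospital: categories 5 and above are all worded as hospitalized, so such a patient could be scored 1 or 2.

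**3. When would a status be carried forward?** SAP 7.4 uses the last earlier assessment only where nothing was collected at the time point for a reason other than death. Both the progression item and the Day 29 clinical outcomes/WHO data would have to be absent. In that case:

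- From Day 10, the last earlier mark on the Progression Endpoint row: 29 − 10 = 19 days.
- With the table a) windows of 2 days either side at both visits: 27 − 12 = 15 to 31 − 8 = 23 days.
- For table b) patients, using the clinical outcomes/WHO mark at Day 15: 29 − 15 = 14 days.

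The same SAP section treats a patient last seen at score 1 or 2 as recovered through Day 29, so for discharged patients the assumption would be favourable.

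**4. Weight of one misclassified patient.** With the protocol's 10 alvelestat and 5 placebo patients: 1/10 = 10 and 1/5 = 20 percentage points. The SAP instead states 1:1 allocation with 7-8 per arm: 1/8 = 12.5 and 1/7 = 14.3 percentage points.

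**5. Baseline.** The Day 1 cell of the Progression Endpoint row is blank in table a), against Section 5.1. Table b) starts at Day 6 and has no Baseline column. The endpoint is a proportion on a fixed day, so no Baseline value enters its calculation.

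**The case against.** The strongest reply is that the Day 29 information is already scheduled. The Day 29 visit is itself named the Clinical Outcome Assessment. The clinical outcomes row is worded to include the WHO scale rather than to consist of it. Section 5.1 calls disease progression a clinical outcome, and Section 9.3 places both the progression status and the WHO scale under clinical outcome measurements. On that reading the marked row already carries the item. Section 5.1 also says outright that respiratory support is collected to Day 29, and nothing in the schedule forbids it. The endpoint is exploratory, in a single-center pilot of 15.

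Most of this stands, and it limits the consequence. It does not remove the inconsistency. At Days 5, 10 and 60 the schedule marks both rows, so the progression status is treated there as an item that the clinical outcomes row does not replace. No rule deriving it from the WHO score is written down.

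Three stronger readings are tempting and unsupported:

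- A reader might infer that Day 29 status goes uncollected for all 15 patients. The scheduled WHO score and Section 5.1 contradict that.
- A reader might infer a gap of 60 − 10 = 50 days. That describes this row alone and ignores the scheduled Day 29 visit.
- A reader might infer that Baseline is missing from both tables and is needed. Table b) has no such column, the WHO score is scheduled at Day 1 in table a), and the endpoint does not use a Baseline value.

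**Conclusion.** The inconsistency is real. The row named for the progression endpoint omits Day 29 in both tables, contrary to the endpoint definition and to Section 5.1. It is an omission in the schedule, not a flaw in the endpoint, and it is worth correcting because the correction is exact and nearly free.

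The practical loss is small provided that the Day 29 WHO score is obtained as scheduled and that high-flow or non-invasive support outside hospital is rare. The documents give no frequency for the latter. If the Day 29 data were missing as well, a status about 19 days old could stand in for the endpoint, and one wrong patient would shift an arm's proportion by 10 or 20 percentage points under 2:1 allocation. The blank Baseline cell in table a) is a secondary conflict with Section 5.1 and has no effect on the endpoint.

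**What to change.** - In both schedule tables, mark the Progression Endpoint row at Day 29 with footnote 5, so that a telehealth contact suffices after discharge. The row then covers Days 5, 10, 29 and 60 in table a) and Days 10, 29 and 60 in table b).
- Record the Section 9.3.1 status and the level of respiratory support directly at the Day 29 contact, wherever the patient is. Take death from the recorded date of death.
- State in the protocol and SAP the back-up rule for when the direct item is missing: WHO 0-4 is alive and free of respiratory failure, and 5-8 is not. This follows the protocol's definition. SAP 8.4.2 names only invasive ventilation or ECMO, which would put score 5 on the other side of the cut, so that wording needs to be aligned at the same time.
- Reconcile the Baseline cell of table a) with Section 5.1, either by marking it or by saying that the Day 1 WHO score serves.

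The cost is one cell in each table, the Baseline cell or a clarifying sentence, one case report form item at a contact that already takes place, and a sentence in each document for the back-up rule. No extra visit is needed.

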3.0 INTRODUCTION

3.1 Background

Infection with the SARS-CoV-2 virus has led to the coronavirus disease 2019 (COVID-19) pandemic, affecting global health and economies on an unprecedented scale (Zhu et al 2020; Holshue et al 2020; Goyal et al 2020). The spectrum of illness ranges from asymptomatic to critical, with mild symptoms in ~80% of cases. However, severe disease is characterized by dyspnea, hypoxemia, and respiratory failure with acute respiratory distress syndrome (ARDS), shock, and multi-organ failure. As of June 10, 2020, the World Health Organization reported that there are over 7.2 million cases of COVID-19 worldwide, accounting for nearly 413,000 deaths (World Health Organization | COVID-19 Situation Report 142, June 2020). While the use of stay-at-home orders, social distancing, and deployment of limited business models have resulted in a “flattening of the curve”, the number of new cases and deaths continue to rise and there are limited therapeutic options. To date there are no approved therapies for SARS-CoV-2 infection, though antiviral medications have shown the most promise (Grein et al 2020; Cao et al 2020). Other strategies have included targeting host inflammatory pathways or repurposing existing medications, but these have not been successful in early trials (Geleris et al 2020; Ingraham et al 2020; Mercuro et al 2020). Emerging data demonstrated reduced mortality with use of dexamethasone from a placebo-controlled trial (Horby et al 2020). The evidence of immunopathogenesis of COVID-19 disease supports the potential of intervention with immunomodulators in addition to the efforts in anti-viral therapy.

3.2 Study Rationale

The clinical course of COVID-19 is characterized by initial symptoms typical of viral infection. In some individuals, this is followed several days later by rapid deterioration, concurrent with the onset of the immune response (Ingraham et al 2020). An acute innate inflammatory response is typical, with elevated pro-inflammatory cytokines, marked elevation of acute phase reactants and cytokine storm. Available therapies consist of organ support, anti-coagulation to reduce risk of venous and arterial thrombosis, and as needed treatment of infection and sepsis. Repurposed’ existing immunomodulating therapies are being progressed through global ‘platform’ trials, including for anti-IL6, anti-IL1, dexamethasone and hydroxychloroquine, with results emerging. None are specifically targeting neutrophil-driven pathogenic mechanisms.

Neutrophils and neutrophil extracellular traps (NETs) have recently been established as a central feature of SARS-CoV-2 pathogenesis, and NETosis is associated with poor outcomes in patients hospitalized with COVID-19 (Zuo et al 2020; Barnes et al 2020). Levels of NETs correlate with disease severity in ALI/ARDS outside of COVID-19. NETs are networks of extracellular DNA fibers, histones, myeloperoxidase (MPO) and neutrophil elastase (NE), released from neutrophils and involved physiologically in capturing bacteria. However, if uncontrolled, NETs are cytotoxic to endothelial and epithelial cells; acting as Damage Associated Molecular Pattern Molecules (DAMPs), promoting cytokine release and thromboses (Kim et al 2019). Neutrophil elastase is essential to NET formation (Papayannopoulos et al 2010) and remains active when decorating

the NET fibers. The physiological inhibitor of NE is Alpha-1 antitrypsin (AAT), but studies in COVID-19 have shown this to be overwhelmed ([McElvaney et al 2020](#)) and treatment with NE inhibitors have potential to impact the disease progression to ARDS through disruption of NETosis. In experimental models of ARDS, alvelestat, the NE inhibitor proposed for this clinical trial, protected the lung from inflammation and injury through NET inhibition ([Li et al 2018](#)). There is evidence from clinical efficacy studies using NE inhibitors in ALI/ARDS. Sivelestat ('Elastpol') is a selective human NE inhibitor that is approved in Japan and South Korea for the treatment of ALI/ARDS accompanied by Systemic Inflammatory Response Syndrome. A meta-analysis of 6 randomized controlled trials in patients with all forms of ALI/ARDS, did not demonstrate an effect on mortality, Intensive Care Unit or ventilator days. However, a sensitivity analysis detected a significant improvement in oxygen deficit measured by $\text{PaO}_2/\text{FiO}_2$ (Standardized Mean Difference (SMD): 0.87; 95% CI: 0.39 to 1.35; $p < 0.001$ ([Pu et al 2017](#)) and oxygenation at Day 3 ([Iwata et al 2010](#)). Sivelestat appeared to have an effect on mortality in ARDS associated with disseminated intravascular coagulation ([Miyoshi et al 2014](#)), which is more closely aligned with pathogenic processes in COVID-19, and provides support for the NE mechanism.

Alvelestat is an oral, specific, NE inhibitor, with experience in over 1000 healthy volunteers and patients with lung disease. There has been evidence of mechanistic effect in 4-week duration clinical studies of neutrophil-driven diseases (significant decrease in biomarkers of elastase activity and inflammation in cystic fibrosis ([Elborn et al 2012](#)), and clinically significant improvement in lung function and inflammation in bronchiectasis ([Stockley et al 2013](#))). A scientific rationale for NE inhibition in SARS-CoV-2 infection, plus the established safety profile for alvelestat supports investigating alvelestat in COVID-19. Here, we propose a pilot randomized control trial assessing the safety and tolerability and exploring biomarkers of efficacy and clinical outcomes, by comparing alvelestat on top of standard of care compared to placebo on top of standard of care in patients hospitalized with COVID-19.

The specific objectives of this study are to evaluate the safety and tolerability of alvelestat in this first time in disease study, confirm PK and explore evidence for mechanistic effect on NETosis and clinical outcomes in patients with COVID-19 respiratory disease. The pathogenesis of COVID-19 is complex, where multiple pathogenic mechanisms are in play and this study will explore the potential role of NE inhibition. Positive data from this Phase Ib/II trial will support progression to a formal dose-ranging efficacy study, informed by safety, tolerability and PK in the COVID-19 population.

Alvelestat is a potent and specific inhibitor of NE, has predictable PK and an established PK/PD relationship in *ex vivo* neutrophil elastase inhibition ([Gunawardena et al 2013](#)). This enables a dose to be chosen to fully test the mechanism in COVID-19 disease. Relevant blood biomarkers will be used to detect signals of effect. Blood biomarkers of NETosis, cell-free DNA (cf-DNA), citrullinated-H3 and MPO-DNA complexes are available. These are elevated in hospitalized COVID-19 patients and correlate with disease severity Cell-free -DNA and MPO-DNA complexes correlate with acute phase response, C-reactive protein, D-dimers, and neutrophil

count, whereas citrullinated-H3 with platelet count (Zuo et al 2020). Neutrophil elastase activity is measurable by the elastic breakdown product desmosine/isodesmosine, Effects on markers of inflammation, proinflammatory cytokines (IL-1beta, IL-6, IL-8 and TNF-alpha) and coagulopathy (d-dimer) will explore whether the inhibitory effect of alvelestat on neutrophil elastase/NETs delivers potential benefit on the downstream inflammatory and vascular processes. These mechanistic effects data in combination with safety and tolerability and predictability of PK, will be used to make progression decisions on alvelestat development in COVID-19 disease.

